**Figure 3: Study Design**

## 7.2 Discussion of Study Design, Including the Choice of Control Groups

In order to accustom patients to the conditions they will encounter during the treatment portion of the study, during the pain observation period study medication will be administered under single-blind conditions (i.e site staff will be aware that placebo is being dispensed, but this will not be revealed to patients, who will not know whether they are receiving active drug or placebo during the pain observation period). The randomized treatment portion of the study is designed as a double-blind, placebo-controlled study for the initial ~12 weeks. As noted above, because expectancy and other non-specific improvements are commonly seen in studies of pain drug efficacy, the use of placebo rather than active comparator is required to provide a definitive understanding of whether observed improvement is or is not treatment-specific. Placebo is justified on the scientific grounds of ensuring that the results of the study are interpretable, and is acceptable ethically as 1) there is no convincing evidence that the available active treatments change the course of the disease, and thus patients are not put at additional risk for disease worsening or long-term harm by not administering currently available treatments for a limited periods; and 2) rescue medication for acute episodes of pain is permitted in this protocol to ensure that patients are not at risk for excessive discomfort.

While some effects in animal models appeared rapidly after dosing, in patients with diabetic neuropathic pain, ricolinostat's proposed mechanism of action (restoration of axonal transport with consequent improvement in synaptic function and reduction in aberrant pain signaling) could require a longer period of time to reach its full effect, particularly as most patients will have had chronic pain with longstanding changes in peripheral nerve function; such chronic changes may require more extended treatment to reverse. Therefore, this study incorporates an acute (~4-week) as well as longer (~12-week) assessment of efficacy. This will allow characterization of the course of response as well as the stability of response over time, will inform the design of future studies, and is consistent with regulatory requirements for registration endpoints in pain studies in which an efficacy assessment at 12 weeks is generally required. The

treatment durations planned for this study are supported by acute and chronic toxicology studies in animals that did not predict serious safety concerns in humans (details available in the Investigator's Brochure), and the available safety and tolerability data from studies of ricolinostat in patients with hematologic malignancies also did not suggest serious safety or tolerability concerns during either short or long-term treatment. The ~12-week open label Safety Extension will allow further assessment of safety and tolerability, which is important as drugs to treat diabetic neuropathic pain are generally used on a long-term basis.

In animal models, ricolinostat has been shown to reverse pathological reductions in IENFD. IENFD is also reduced in patients with diabetic neuropathy, and drug-induced increases in intraepidermal nerve density may represent a biomarker predictive of efficacy. Therefore, change from baseline to endpoint in IENFD will be measured in patients participating at a selected subgroup of sites.

### **7.3 Selection of Study Population**

Patients with Type 1 or Type 2 diabetes suffering from painful distal symmetric sensorimotor polyneuropathy (painful DPN) present for at least 6 months (to ensure that symptoms are stably present) will be eligible to participate if they meet all inclusion and exclusion criteria. The diagnosis will be confirmed by the Investigator through medical history and physical examination as established by medical history and physical examination.

#### **7.3.1 Inclusion Criteria**

Eligible patients will meet the following criteria:

1. Able to understand the study's purpose and requirements, and able to voluntarily provide informed consent to participate.
2. Age  $\geq$  18 years and  $<$  80 years at the time of signing the ICF.
3. FOCBP must agree to use reliable contraceptive methods for the duration of the study and for at least 3 months after completing treatment with study drug. For the purposes of this study, reliable methods of contraception include abstinence, oral contraceptives, hormonal contraceptive implants such as Nexplanon, hormonal vaginal ring such as NuvaRing, intrauterine devices in place for at least 3 months, or barrier methods used in conjunction with spermicide. To be considered post-menopausal and of non-child-bearing potential, women less than 60 years with less than 2 years since their last period must have FSH  $>$  40 IU/L and estradiol  $<$  20 pg/mL unless on hormone replacement.

Male patients participating in the study must also agree to use these reliable contraceptive methods if sexually active with a FOCBP partner and also agree to abstain from sperm donation from Day 1 through 3 months after completing treatment with study drug.

4. Type 1 or Type 2 diabetes of at least 6 months duration that meets American Diabetes Association criteria (American Diabetes Association, 2020) with an HbA1c > 6.5% at the time of Screening. If the HbA1c at the time of Screening is less than 6.5%, evidence that the patient meets American Diabetes Association criteria for diabetes must be documented and reviewed with the Sponsor prior to entering the patient in the study. Additionally, the diabetes should be adequately controlled, with an HbA1c < 11% and no evidence of severe hypoglycemia requiring hospitalization within the past 6 months, and in the Investigator's judgment sufficiently stable to allow participation in the study.
5. Painful distal symmetric sensorimotor polyneuropathy due to diabetes as defined by having 1 or more relatively symmetric, distally accentuated (stocking or stocking-glove) neuropathic symptom(s) and 1 or more relatively symmetric, distally accentuated (stocking or stocking-glove) neuropathic sign(s), except that diminished reflexes are not, in the absence of at least 1 other neuropathic sign, sufficient to make the diagnosis. Neuropathic symptoms can include pain, numbness, tingling, or weakness in a distal to proximal (stocking and glove) distribution; signs can include impaired pinprick, light touch, vibration, or position sense. The neuropathy must have been present (by history) for at least 6 months and must be confirmed and documented by the Investigator based on clinical history and physical examination.
6. DN4 score  $\geq 4$ .
7. Meets initial diary criteria during the 14 days in the Pain Observation period as determined by an algorithm that includes diary compliance, overall level of pain, and day-to-day variability in pain, including at least 5 of 7 daily entries completed the 7 days prior to Day 1, and a mean intensity and standard deviation within a pre-specified bound (the precise bounds are held as double-blind to avoid introducing bias into the ratings). Additionally, at least 5 of 7 doses of placebo must be taken the 7 days prior to Day 1 as prescribed during the Pain Observation period for patients to be eligible to continue in the study.
8. Able to adhere to the study visit schedule and other protocol requirements.

### 7.3.2 Exclusion Criteria

Patients meeting any of the following criteria will be excluded from the study:

1. Females who are pregnant or lactating.
2. Extremely overweight, defined as  $BMI > 40 \text{ kg/m}^2$ .
3. Difficulty understanding instructions for diary use as determined by the Investigator or other issues that are likely to make compliance with study requirements difficult.

4. Presence of any neuropathy other than DPN and/or significant risk factors for neuropathy other than diabetes, including Charcot Marie Tooth disease; alcohol abuse; B12 deficiency not adequately treated; uncontrolled hypothyroidism; evidence of paraproteins by serum immunofixation; history of chemotherapy with neurotoxic agents such as platinum analogs, taxanes, vinca alkaloids, eribulin, bortezomib and other proteasome inhibitors; or immunomodulatory agents such as thalidomide, lenalidomide, pomalidomide, neurotoxic check-point inhibitors, or any other chemotherapy known to have neurotoxic effects.
5. Other pain conditions that could confound the results of this study, or other chronic pain condition(s) that could affect compliance with pain medication restrictions or confound pain assessments. In addition to a general history and clinical examination, this will be assessed using the MDT. Patients who screen positive on this tool for a potentially confounding disorder must be discussed with and approved by the Sponsor's Medical Monitor prior to being randomized into the study.
6. Painful DPN patients who have undergone lower limb amputations, are non-ambulatory, or whose walking is so impaired as to require a walker or other assistance for ambulation. Individuals whose neuropathy is so severely advanced as to create a significant risk that the neuropathy will be poorly responsive to treatment as defined by a UENS score > 24 at the time of Screening are also excluded from participation.
7. Have met DSM V criteria for opioid use disorder or DSM V criteria for alcohol use disorder (moderate or severe) within the past 2 years.
8. Opioid use at a dose of  $\geq$  30 morphine milligram equivalents on 3 or more days a week during the month prior to Screening.
9. Active suicidal ideation or suicidal behavior as assessed by the Investigator and/or by a rating of 3 or greater on the C-SSRS (see [Appendix II](#)).
10. The use of marijuana or CBD during the 30 days prior to starting study drug.
11. A positive urine screen for illicit or non-prescribed controlled substances at baseline.
12. Have been using non-drug interventions for pain (eg, acupuncture, mindfulness therapy, etc) for at least 3 months prior to starting study drug may continue these interventions, however such treatments may not be initiated during the study, and any patients who plan to initiate such treatment during the study are excluded from participation.
13. Repeated use (greater than 3 occasions) of over-the-counter capsaicin on extremities within 3 months of Screening or prescription Qutenza use within 6 months of Screening.
14. Implanted medical device (eg, spinal cord stimulator, intrathecal pump, or peripheral nerve stimulator) for the treatment of pain.

15. Has a QT interval corrected for heart rate using Fridericia's formula (QTcF)  $> 450$  msec (male) or  $> 460$  msec (female) or  $> 480$  msec with right bundle branch block on 12 lead ECG at Screening, or requires treatment with drugs known to prolong the QT interval (including azithromycin, chloriquine/mefloquine, clarithromycin, droperidol, erythromycin, moxifloxacin and sevoflurane), or has a known history of torsade de pointes or congenital long QT syndrome.
16. Family or personal history of long QT syndrome or ventricular arrhythmias including ventricular bigeminy, previous history of QT prolongation not attributable to an identified and transient cause, or need for treatment with medications associated with QT prolongation.
17. Hemoglobin  $< 11.5$  g/dL (female) or  $< 13$  g/dL (male), total white blood cell count  $< 2500/\text{mm}^3$ , neutrophil count  $< 1250/\text{mm}^3$ , lymphocyte count  $< 1000/\text{mm}^3$ , or platelet count  $< 100,000/\text{mm}^3$ .
18. eGFR of  $< 45$  mL/min/1.73 m^2 (ie, patients with stage 3b or more severe renal disease are excluded).
19. Serum bilirubin values  $> 2.0$  mg/dL. Individuals with known hereditary benign hyperbilirubinemia (Gilberts' syndrome) and a bilirubin  $< 3.0$  may participate in the study after discussion and agreement with the Sponsor's Medical Monitor.
20. Serum ALT or AST values  $> 1.5 \times$  the ULN.
21. Known HIV positive or active hepatitis virus (A, B, or C) infection.
22. Participation within 1 month of Screening in a clinical trial involving treatment with an investigational product. Concurrent participation in an observational study (ie, no investigational treatment being used) is allowed provided it does not interfere with the procedures and conduct of this protocol.
23. Any serious medical condition or comorbidity, laboratory abnormality, or psychiatric illness not otherwise specified that could place the patient at undue risk during trial participation, that could confound the results of the study, or that could reasonably be expected to affect patient compliance with study requirements for treatment and evaluation, as judged by the Investigator.
24. Any known recent exposure within the 14 days prior to initial Screening to COVID-19 or symptoms of COVID-19 infection or other reason to suspect COVID-19 infection as assessed by the Investigator at the time of initial Screening.

Note: Abnormal Screening laboratory values that appear to be spurious (eg, laboratory error), or that are the result of an identified transient event that if resolved is unlikely to recur, may be repeated once. Should this occur, the Investigator should document the reason for repeating the test, and if the repeat examination is within the acceptable range, the patient may participate.

## **7.4 Randomization and Blinding**

### **7.4.1 Patient Identification**

After giving informed consent, study candidates will be registered in the Medpace Interactive Response Technology (IRT) and assigned a unique identification number (i.e., patient number). Patients will not be randomized until all Screening, Washout, Pain Observation, and Pre-Treatment/Day 1 procedures are completed. The assigned patient number will be used throughout the study on all records for identification purposes.

### **7.4.2 Randomization**

Patients will be randomized 1:1 to receive either ricolinostat or placebo. The randomization schedule will be computer-generated and a blocked randomization by site with varying block sizes will be utilized. Specific block sizes will not be disclosed.

Once a patient is confirmed to be eligible on Day 1, and all Pre-Treatment procedures have been completed, treatment assignment (active or placebo) will be requested using the IRT. After entering the patient number and responding to the eligibility questions, a randomization number that corresponds to the treatment kit(s) will be assigned by the IRT.

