### 3.0 SYNOPSIS

Protocol Number:	REGY-DN-201
Title of Study:	A Phase 2, Randomized, Double-Blind, Placebo-Controlled, Parallel Group Study of Ricolinostat in Patients with Painful Diabetic Peripheral Neuropathy
Study Phase:	Phase 2
Number of Study Sites:	Approximately 50 investigative sites in the US
Study Objectives:	The primary objective of this study is to evaluate the safety and efficacy of ricolinostat compared with placebo for painful diabetic peripheral neuropathy (DPN) as measured by an 11-point numerical pain rating scale (NRS) after 12 weeks.

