### 10.3.3 Primary Efficacy Outcome Measures

The null hypothesis is that there is no difference between the average change from baseline in the NRS score in the ricolinostat and placebo groups; the null hypothesis is stated as  $H_0: \Delta_R = \Delta_P$ , where  $\Delta_R$  denotes the average change from baseline in the NRS score in the ricolinostat group and  $\Delta_P$  denotes the average change from baseline in the NRS score in the placebo group. The alternative hypothesis is stated as  $H_A: \Delta_R \neq \Delta_P$  with a two-sided significance level of 0.05.

The primary estimand for this study is defined by the following attributes:

Estimand attribute	Description
Population	Full analysis set population, which consists of all patients who receive at least one dose of study drug and have baseline average pain intensity score and at least one post-baseline average pain intensity score.
Endpoint	Weekly mean of daily average pain based on the 11-point NRS.
Intercurrent events	All observations in patients who are on stable permitted concomitant pain medication for DPN and who started at least 3 months prior to Screening will be included. If there is a dose change, pain scores after the dose change will be considered missing and will be imputed using Medical Administration Record (MAR) assumption.
Summary measure	Difference between ricolinostat arm and placebo arm as measured by change from baseline in average pain at Week 12.

The primary estimand is the difference in the mean change from baseline through Week 12 in the average pain as measured by the NRS. Patients will record their average pain and worst pain on a daily basis in a diary starting seven days prior to randomization through the end of the study using the NRS, where 0 represents no pain and 10 represents worst possible pain. The baseline average pain score is the mean of the average daily pain scores recorded from day -7 to -1 of the study. (Note: For visits prior to randomization, study day=visit date-randomization date. For visits after randomization, study day=visit date-randomization date+1.) The weekly mean of the average pain will be calculated when four or more daily average pain scores exist for that week. If a patient has fewer than four daily average pain scores in a week, then the weekly mean pain will be set to missing for that week.

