A MMRM approach will be used to analyze the change from baseline to Week 12 in the average NRS pain score, with the mean change from baseline in the average NRS pain score at each week as the outcome in the model. The model will include the following covariates: treatment, visit, treatment by visit interaction, baseline NRS pain score, baseline NRS pain score by visit interaction, and use of concomitant medication for painful DPN (yes vs. no). The within-patient correlation will be modeled by using an unstructured covariance matrix. If the model does not converge, then a Toeplitz covariance structure will be used, which assumes that observations closer together are more correlated than those further apart in time. If convergence

is still not attained, then the auto-regressive of order one will be used, which has the same assumption as the Toeplitz model but is more restrictive. If the model still does not attain convergence, then compound symmetry variance-covariance models will be used, which assume equal correlation between measurements from a patient. Restricted maximum likelihood will be used as the method of estimation with the degrees of freedom approximated using the Kenward Rogers approach. The primary estimand will be obtained from this model.

It is assumed that short-term action of rescue medication does not affect the average daily pain score and scores that are collected during the use of rescue medication will be used in the analysis. Patients on a stable dose of permitted concomitant medication that has been started at least 3 months prior to starting the Pain Observation period will be included in the analysis. However, if there is a dose change, the pain scores after dose change will be set to missing and imputed under the assumption of MAR.

In order to assess the robustness of the primary analysis, the following additional sensitivity analyses will be performed:

1. A tipping point analysis with multiple imputation, in which the missing values in the ricolinostat arm will be assigned a shift parameter during imputation in order to determine the point where statistical significance changes.
2. An MMRM analysis with jump to reference, in which all missing values are imputed based on the placebo arm. This is a worst-case scenario where missing values among patients in the ricolinostat arm are imputed as if they came from the placebo arm.
3. An MMRM analysis using MAR and monotone missing assumptions.

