#### **3.2. Study population**

This study will enroll patients at up to 50 sites in the United States. Patients with Type 1 or Type 2 diabetes suffering from painful distal symmetric sensorimotor polyneuropathy (painful DPN) present for  $\geq 6$  months who meet all inclusion and exclusion criteria are eligible to participate. Eligible patients will be randomized in a 1:1 ratio to receive either ricolinostat or placebo.

Exhibit 1 and Exhibit 2 display the study's inclusion and exclusion criteria, respectively.

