### **7.2. Identification of the primary model**

The primary endpoint is change from baseline in mean average pain intensity over the 12 weeks of treatment as measured by the weekly average NRS in the FAS population. The primary endpoint will be analyzed using a MMRM analysis. The MMRM will be fit with the weekly mean change from baseline in the NRS score at Weeks 1, 2, 4, 8 and 12 as the outcome. The following covariates will be included in the model: baseline NRS score, visit, treatment group, concomitant medication for painful DPN (yes vs. no), treatment group by visit interaction term, and baseline NRS score by visit interaction. A restricted maximum likelihood will be used as the method of estimation with the degrees of freedom approximated using the

Kenward Rogers approach (see Table 4 for an example of the MMRM code to be used for the primary model). The model will be fit with an unstructured covariance matrix. If the MMRM with an unstructured covariance matrix does not converge, the following covariance structures will be substituted in the order listed below. Each subsequent covariance structure will be used only if each previous covariance structure fails to converge. The covariance structure for the final model will be the first structure in the sequence that produces a stable model that converges.

1. Toeplitz covariance structure (assuming measurements taken closer together in time are more highly correlated than those taken farther apart).
2. First order auto-regressive (AR[1]) covariance structure (assuming measurements taken closer together in time are more highly correlated than those taken farther apart, but more constrained than the Toeplitz structure).
3. Compound symmetry covariance structure (assuming equal correlation for measurements from a patient, regardless of how far apart in time when they were taken).

Once the primary model is established, this model will be used for all analyses.

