**Table 4. SAS code for MMRM analysis as part of the imputation process**

---

```

proc mixed data=COMBINE method=reml alpha=0.025 covtest;
  by _IMPUTATION_;
  class AVISITN(ref=LAST) TRT USUBJID CONMED;
  model DELT_NRS = BASE_NRS CONMED TRT AVISITN TRT*AVISITN
    BASE_NRS*AVISITN/ solution ddfm=kr;
  repeated VISITNUM / subject=USUBJID type=TBD r;
  estimate 'RIN - PBO AT WK 12' TRT 1 -1
    TRT*AVISITN 0 0 0 0 1 0 0 0 0 -1
    / CL;
  lsmeans TRT*AVISITN/diff;
  ods output estimates=SI_ESTIMATES;
run;

```

---

The analysis outlined in Table 4 will produce 100 estimates of the difference between the ricolinostat and placebo groups in change from baseline in NRS at Week 12. These values are contained in SI\_ESTIMATES. Note that the “type =” option in the repeated statement will need to be modified to include the covariance structure that is selected for the primary model. The output from the estimate statement should be compared to that of the lsmeans statement to ensure that the correct comparison is selected. Table 5 provides the code for the implementation of Rubin’s rules to obtain the combined estimates of treatment effect at the two dose levels.

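### Site is the only randomisation stratum but is in no efficacy model; if outcomes correlate within site, the analysis is mildly conservative and forgoes a little power

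*Protocol*

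**What the plan says.** **Design.** Protocol 7.4.2: "Patients will be randomized 1:1 to receive either ricolinostat or placebo", and "a blocked randomization by site with varying block sizes will be utilized". Site is the only stratum named. The synopsis gives "Approximately 50 investigative sites in the US"; SAP 3.2 says "This study will enroll patients at up to 50 sites in the United States".

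**Primary model.** Protocol 10.3.3: "The model will include the following covariates: treatment, visit, treatment by visit interaction, baseline NRS pain score", followed by the baseline-by-visit interaction and use of concomitant medication for painful DPN. SAP 7.2 lists "baseline NRS score, visit, treatment group, concomitant medication for painful DPN (yes vs. no), treatment group by visit interaction term" and the baseline-by-visit interaction. The code in SAP Table 4 begins "model DELT_NRS = BASE_NRS CONMED TRT AVISITN TRT*AVISITN"; its only clustering is the repeated statement within patient. None of these has a site term, fixed or random.

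**Other analyses.** SAP 8.1 carries the Section 7 approach over to NRS at Week 4 and to UENS. SAP 9 uses the SAP 7.2 model for worst pain, BPI-SF, NTSS-6 and QOL-DN, and the primary approach for weekly rescue use. The sensitivity analyses in Protocol 10.3.3 and SAP 7.4 vary only the handling of missing data. No section explains why site is left out. SAP 1 makes the SAP govern where the two documents differ.

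**The concern.** Blocking within site nearly equalises the arms at each site, so differences between sites largely cancel out of the treatment contrast. A model without site does not know this and leaves the between-site variation in its residual. If such variation exists, the reported standard error exceeds the true one, intervals are wider than the design warrants, and the test runs below its nominal level. The plan adjusts for concomitant medication, which is not a stratum, and omits the one factor that the design balances.

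Some site effect is plausible here. Protocol 5.5 notes that pain ratings are open to expectation effects. Protocol 7.2 says site staff know that the lead-in is placebo. Repeat rating training at some visits is left to the investigator (Table 1, note 13). UENS is scored by physical examination. These points make a non-zero correlation credible but do not give its size. At stake is some efficiency and calibration, not the validity of the trial.

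**Working it through.** **Inputs from the documents.** N = 274 (137 per arm), difference 0.8, SD 2.35, power 0.80 (Protocol 10.3.1, SAP 6.1.1); test "with a two-sided significance level of 0.05" (Protocol 10.3.3); about 50 sites, so 274/50 ≈ 5.5 patients per site.

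**Assumptions.** The ICC of the Week 12 change, the block sizes and the spread of site sizes are not in the documents. The SD of 2.35 is read as the total SD, including any between-site part.

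**Step 1: the plan's own figure.** SE = 2.35 × √(2/137) = 0.284. Power = Φ(0.8/0.284 − 1.96) = 0.804. An exact t-test gives 137 per arm, N = 274 and power 0.802. The stated figure reproduces, with no credit taken for site.

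**Step 2: approximation with near-complete balance within site.** The true SE is 0.284 × √(1−ICC), while the model without site still reports 0.284.

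- Overstatement of the SE: 1/√(1−ICC)
- Type I error without site: 2[1 − Φ(1.96/√(1−ICC))]
- Power without site: Φ[(0.8 − 1.96 × 0.284)/(0.284√(1−ICC))]
- Power with ideal adjustment: Φ[0.8/(0.284√(1−ICC)) − 1.96]

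| Assumed ICC | SE too large by | Type I error | Power without site | Power, ideal adjustment | Gain (points) |
|---|---|---|---|---|---|
| 0 | 0% | 5.0% | 80.4% | 80.4% | 0 |
| 0.02 | 1.0% | 4.8% | 80.7% | 81.2% | 0.5 |
| 0.05 | 2.6% | 4.4% | 81.1% | 82.4% | 1.3 |
| 0.10 | 5.4% | 3.9% | 81.7% | 84.4% | 2.7 |

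**Step 3: simulation.** 50 sites, 274 patients, 1:1 blocks within site (2/4 or 4/6), equal or uneven site sizes, one Week 12 outcome, 4,000 replicates per setting. The uneven-site, 4/6-block setting was not completed at ICC 0.10. Power for uneven sites with blocks of 2/4:

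| ICC | No site | About 50 fixed effects | Random site |
|---|---|---|---|
| 0 | 0.802 | 0.784 | 0.806 |
| 0.02 | 0.803 | 0.791 | 0.809 |
| 0.05 | 0.805 | 0.802 | 0.818 |
| 0.10 | 0.813 | 0.827 | 0.838 |

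Across the settings run:

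- The random effect gained about 0.5-1 point at ICC 0.02, 1-1.5 at 0.05 and 2.5-3 at 0.10.
- At ICC 0.10 the model without site reported an average SE of about 0.283 against an empirical 0.271-0.276, with type I error 0.036-0.042.
- Fixed effects lost about 1-2 points at ICC 0, lost up to 1.5 at 0.02, were about neutral at 0.05, and gained only from about 0.10.

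At ICC 0 the random-site model should be read as neutral, not better. Its type I error was 0.045-0.057, against 0.045-0.055 without site. Monte Carlo error is about ±1.2 points on each power figure, but the three analyses were run on the same simulated data, so their differences are steadier than that.

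A further simulation (6,000 replicates per setting) pooled sites with fewer than 8 patients into one fixed stratum. It gained about 0 points at ICC 0-0.02, 0.9 at 0.05 and 1.6 at 0.10.

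**The case against.** The case for leaving the model alone has five parts.

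1. *The effect is conditional.* It needs a non-zero ICC, and the relevant one is what remains after baseline pain and concomitant medication are in the model. This stands. A reader might infer that the standard errors are too large as a matter of fact; the documents do not support that, because they give no ICC.
2. *Nothing planned is lost.* A reader might also infer that the trial is underpowered or its primary test invalid. Neither follows. The sample size takes no credit for site, power without site does not fall below plan at any ICC in the table, and the error is conservative, so a positive result is not threatened. This stands too.
3. *Adjustment is not free.* Unpooled fixed effects can cost power, and pooled ones recover only part of the gain. A random effect adds a convergence question. The imputation models in SAP Tables 2 and 3 contain no site, and including about 50 sites by arm would leave roughly three patients per cell. This limits the form of the fix but does not remove the case for a random intercept.
4. *Adjusting the ANCOVA models is the wrong target.* The protocol uses ANCOVA for UENS, BPI-SF, NTSS-6 and QOL-DN, but the governing SAP analyses them by mixed model. Correct, and the fix below follows the SAP.
5. *The blinded review can settle it.* SAP 5.1 lets methods be finalised before unblinding. It does not name site, so the omission is not cured unless the term is written in.

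**Conclusion.** The omission is real and unexplained: site defines the randomisation and appears in no efficacy model. Its consequence is modest and conditional. For ICCs of 0.02 to 0.10 the standard error is at most 1.0% to 5.4% too large, the type I error is about 4.8% to 3.9%, and a random site effect would recover about 0.5 to 3 points of power. At ICC 0 there is no loss. The analysis as planned is valid and conservative, and 80% power at 274 patients is intact.

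These sizes rest on an assumed ICC, assumed block and site sizes, SD 2.35 read as the total SD, and a single Week 12 outcome in place of the full repeated-measures model with multiple imputation. They apply to the random intercept only, not to fixed site effects.

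**What to change.** Add a random site intercept to the SAP 7.2 model and the Table 4 code, and to the analyses that reuse that model: NRS at Week 4, UENS, and the secondary mixed models in SAP 9.

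Pre-state that the term is dropped if its variance is estimated as zero or the model does not converge, and that this is decided before the covariance fallback sequence in SAP 7.2 begins. Making the decision once, at step 1 of SAP 7.1, keeps the same model for all 100 imputed datasets. Do not fit about 50 unpooled fixed site effects. State in the SAP that the imputation models in Tables 2 and 3 do not include site.

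If the sponsor prefers to keep the current primary model, the minimum is a random-site sensitivity analysis in SAP 7.4 or a sentence explaining why site is left out.

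The cost is one model term, one more convergence rule and the note on imputation. No change to sample size or conduct is needed.
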